6.1.3 Randomized-Withdrawal (RW) Period

During the RW period, subjects will continue with once-weekly study drug administration as well as daily 11-point pericarditis pain NRS scoring. Visits will occur every 4 weeks, alternating TC/RN visits and clinic visits, with the first visit during the RW period (RW Week 4) being a TC/RN visit. Additional unscheduled visits may occur at any time for evaluation of suspected pericarditis recurrence ([Section 6.1.6.1](#)) or for other reasons as deemed necessary by the study investigator.

The following procedures are to occur during the TC/RN visits:

Site TC visits:

- Assess for AEs.
- Assess for suspected pericarditis recurrence events.
- Evaluate concomitant medications as well as pericarditis concomitant medications.
- Additional discussion/assessment as needed.
- Confirm and review upcoming visit arrangements.
- Instruct the subject to bring used and unused study drug vials (those not yet obtained by visiting RN) to the next clinic visit.

RN home visits:

- Obtain central laboratory samples for CRP.
- Provide review of self-administration of the study drug as needed.
- Monitor administration of the study drug (whenever possible).
- Obtain used study drug vials and materials.

The following procedures are to occur during the clinic visits (except for Week 24; see below):

- Assess for AEs.
- Assess for suspected pericarditis recurrence events.
- Evaluate concomitant medications as well as pericarditis concomitant medications.
- Record height and body weight.
- Obtain central laboratory samples for chemistry, hematology, and CRP.
- Obtain central laboratory sample for PK and biomarkers (Weeks 8 and 24 only).

- Obtain central laboratory sample for ADAs (Week 24 only).
- Have all subjects complete the PGIPS score.
- The investigator is to complete the PGA-PA.
- Additional discussion/assessment as needed (i.e., remind the subject about daily pericarditis pain NRS entry).
- Obtain used and unused study drug vials for study drug compliance evaluation.

Upon completion of the above study activities, study drug dispensing can commence. The following procedures occur:

- Obtain weight for pediatric drug dispensing and dosing ([Table 5–1](#)).
- Monitor administration of the study drug dose (whenever possible) and have the subject record in the medication diary.
- Dispense study drug through the IWRS and record the amount (number of vials) dispensed.

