4.3.2.1. Discontinuation of Study Drug

The study drug dosing will be permanently stopped if any of the following occurs:

- The subject develops TB or malignancy, excluding non-metastatic cutaneous squamous cell carcinoma or basal cell carcinoma
- Initiation of protocol-prohibited medication (Section 5.6.5)
- Subject requires treatment with CS for pericarditis during RW or LTE periods of the study
- Pregnancy or pregnancy planned during the study or within 3 months after the last study drug administration
- ALT or AST values $\geq 3 \times$ ULN associated with total bilirubin $\geq 2 \times$ ULN, with no underlying medical conditions to explain the elevated values
- Treatment with a live (attenuated) vaccine during the study
- Investigator or Sponsor's medical monitor or [REDACTED] medical monitor decides that, for safety reasons, it is in the subject's best interest
- Termination of the study by Kiniksa Pharmaceuticals

Permanent or temporary study drug discontinuation should be strongly considered at the time if any of the following occurs:

- Subject develops an opportunistic infection.
- Subject develops moderate or severe infection
- Neutrophil count $< 1.0 \times 10^3/\mu\text{L}$
- Isolated ALT or AST values $> 5 \times$ ULN
- Surgical procedure

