6.1.4. Pericarditis Recurrence Assessment: Clinic Visit

If a subject experiences symptoms consistent with pericarditis recurrence, he/she should contact the study Investigator immediately for evaluation (including in the LTE). It is possible that a subject may have assessments performed remotely, however, assessments are also expected to be performed at the study site as soon as possible. Required assessments include:

- Evaluate pericarditis pain on the 11-point NRS.
- Evaluate concomitant medications as well as pericarditis concomitant medications.
- Obtain laboratory samples for CRP (local and central) (the POC device provided by Kiniksa Pharmaceuticals is the preferred method for local laboratory CRP assessment).
- Acquire a 12 lead ECG.
- Acquire a cardiac ECHO per core laboratory imaging parameters; this ECHO is read locally for the purpose of pericarditis recurrence assessment and is then submitted to the ECHO core laboratory for central review.
- Perform an abbreviated physical examination, height and body weight.
- For subjects >18 years, complete the SF-36, EQ-5D-5L, ISI.
- For all subjects, complete the PGIPS score.
- The Investigator is to complete the PGA PA.
- Obtain central laboratory samples for PK, ADAs, and biomarkers.
- Other procedures deemed necessary per the Investigator or delegated site personnel (e.g. MRI for sub-study subjects).

Upon having completed the evaluation, if the Investigator makes a clinical diagnosis that the subject is having a pericarditis recurrence event, he/she should contact the [REDACTED] medical monitor to review and confirm that all assessments have been performed and collected. Upon [REDACTED] medical monitor confirmation of completion of the assessment, the Investigator commences as described in Section 6.2.3.

Subjects treated for a pericarditis recurrence event will continue to follow the same visit schedule described for the RW period (Section 6.1.5).

Source documentation including the assessments and evaluations used to confirm a pericarditis recurrence event, are required to be sent to CEC.

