6.1.5. Randomized Withdrawal Period Visits

During the RW period, subjects will continue with once-weekly study drug administration as well as daily 11-point pericarditis pain NRS scoring. Visits will occur every 4 weeks, alternating TC/RN visits and clinic visits, with the first visit during the RW period (RW Week 4) being a TC/RN visit. Additional unscheduled visits may occur at any time for evaluation of suspected pericarditis recurrence (Section 6.1.4) or for other reasons as deemed necessary by the study Investigator. Refer to Section 13.1 for a comprehensive list of procedures in the Schedule of Activities for these visits.

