7.4. Sample Size Calculations

For the purpose of sample size estimation, time to pericarditis recurrence is assumed to follow an exponential distribution. An event of interest is defined as a subject's first adjudicated recurrence of pericarditis. The following assumptions are used in the sample size calculation using EAST 6.4.1:

- 1-sided significance level 2.5%
- Power 90%
- Median time to event (in weeks) in placebo 8
- Hazard ratio (rilonacept/placebo) 0.244
- Percentage of subjects in the RI period that will not reach RW 10%

Given these assumptions, a total of 22 adjudicated pericarditis recurrence events is required to achieve the power. About 25 subjects per arm (a total of 50 subjects) will be randomized. Considering 10% of subjects in the RI period that will not reach the RW period, approximately 56 subjects will be enrolled in this study.

Patient enrollment and the pericarditis recurrence event accrual will be closely monitored during the study. The monitoring activities will be done in a blinded fashion during the RW period. If the number of patients randomized is less than 50 and/or the time anticipated for the number of events required for the analysis of primary efficacy endpoint significantly exceeds the projected timeline, additional patients may be enrolled and/or randomized at Kiniksa Pharmaceutical's discretion. However, at this time it is anticipated that no more than 100 subjects will be enrolled into this study.

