- m All procedures are to be completed prior to study drug administration.
- n The first dose of study drug is a loading dose. Adult subjects receive 2 SC doses 160 mg (total 320 mg); pediatric subjects (subjects ≥ 12 and < 18 years of age) receive 2 SC doses of 2 x 2.2 mg/kg.
- o Study drug administration is once weekly with a minimum of 5 days required between doses.
- p Randomization and subsequent study drug dispensing to occur after confirmation of Clinical Response (see definition of Clinical Response in Section 6.2.2).
- q The Randomization visit serves as both the RI Week 12 visit and the RW baseline visit.
- s PK and ADA samples will be collected prior to study drug administration. PK at enrollment/baseline will be taken from ADA

Table 3: Study Schedule of Activities – Randomized Withdrawal

Trial Period	RANDOMIZED WITHDRAWAL (event-driven) ^m								END OF RANDOMIZED WITHDRAWAL (EORW) ^t
Visit Name	RW Week 4	RW Week 8	RW Week 12	RW Week 16	RW Week 20	RW Week 24	RW Every 8 Weeks	RW Every 8 Weeks	Per Announced End Date ^u /LTE-Baseline
Visit Window ^b (days)	+/- 2	+/- 2	+/- 2	+/- 2	+/- 2	+/- 2	+/- 2	+/- 2	+/- 7
Visit Type	TC/RN	Clinic	TC/RN	Clinic	TC/RN	Clinic	TC/RN	Clinic	Clinic
Informed Consent Form									X
Concomitant medications	X	X	X	X	X	X	X	X	X
Pericarditis Concomitant medications	X	X	X	X	X	X	X	X	X
Full Physical Examination ^e						X			X
Abbreviated Physical Examination ^d									
Body weight and height		X		X		X		X	X
12-Lead ECG						X			X
Echo ^e						X ^e			X ^e
MRI (substudy only)						X			
Pericardial pain (11-point NRS)	DAILY								
EQ-5D						X			X
SF-36						X			X
ISI						X			X
PGIPS		X		X		X		X	X
PGA-PA		X		X		X		X	X
Hematology, Chemistry Labs (Central)		X				X		X	X
Lipid Panel (Central) ^h						X			X
CRP (Local)									

Trial Period	RANDOMIZED WITHDRAWAL (event-driven) ^m								END OF RANDOMIZED WITHDRAWAL (EORW) ^t
	RW Week 4	RW Week 8	RW Week 12	RW Week 16	RW Week 20	RW Week 24	RW Every 8 Weeks	RW Every 8 Weeks	Per Announced End Date ^u / LTE-Baseline
Visit Window ^b (days)	+/- 2	+/- 2	+/- 2	+/- 2	+/- 2	+/- 2	+/- 2	+/- 2	+/- 7
Visit Type	TC/RN	Clinic	TC/RN	Clinic	TC/RN	Clinic	TC/RN	Clinic	Clinic
CRP(Central)	X	X	X	X	X	X	X	X	X
PK (Central) ^s		X				X			X
ADA (Central) ^s						X			X
Biomarkers (Central)		X				X			
Urine Pregnancy ^j (Local or Central)									X
Urinalysis									X
IWRS Subject Status Update									X
IWRS Weight Input (pediatric only)		X		X		X		X	X
IWRS Drug Dispensing		X		X		X		X	X ^v

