- l Adverse event reporting begins following the subject providing informed consent.
- m All procedures are to be completed prior to study drug administration.
- o Study drug administration is once weekly with a minimum of 5 days required between doses.
- s PK and ADA samples will be collected prior to study drug administration. PK at enrollment/baseline will be taken from ADA. As required, ADA samples will be collected at EOS, ET, and Unscheduled visits.
- z The MRI to occur only if the previous MRI was done longer than 6 months ago.
- aa Visit to occur 18 months from most recent documented recurrence.
- bb Samples collected every 24 weeks.

Table 5: Study Schedule of Activities – Supplemental Visits

Visit Name	PERICARDITIS RECURRENCE ASSESSMENT	END of TREATMENT (EOT) ^x	SAFETY FOLLOW UP (SFU) ^y (6 weeks post last dose)
Visit Window ^b (days)	N/A	N/A	+/- 2
Visit Type	Clinic	Clinic	Clinic or TC/RN
Concomitant medications	X	X	X
Pericarditis Concomitant medications	X	X	X
Full Physical Examination ^c		X	
Abbreviated Physical Examination ^d	X		
Body weight and height	X		
12-Lead ECG	X	X	
Echo ^e	X ^e	X	
MRI (substudy only)		X ^z	
Pericardial pain (11-point NRS)	X	X	
EQ-5D	X	X	
SF-36	X	X	

Visit Name	PERICARDITIS RECURRENCE ASSESSMENT	END of TREATMENT (EOT) ^x	SAFETY FOLLOW UP (SFU) ^y (6 weeks post last dose)
Visit Window ^b (days)	N/A	N/A	+/- 2
Visit Type	Clinic	Clinic	Clinic or TC/RN
ISI	X	X	
PGIPS	X	X	
PGA-PA	X	X	
Hematology, Chemistry Labs (Central)		X	
Lipid Panel (Central) ^h		X	
CRP (Local)	X		
CRP(Central	X	X	
PK (Central) ^s	X	X	X
ADA (Central) ^s	X	X	X
Biomarkers (Central)	X	X	
Urine Pregnancy ^j (Local or Central)			X
Urinalysis		X	
IWRS Subject Status Update	X ^s	X	
IWRS Weight Input (pediatric only)	X		
IWRS Drug Dispensing	X		
Study Drug Compliance Review	X	X	
Assessment of Pericarditis Recurrence	X	X	X
Adverse Event Reporting ^l	X	X	X

- b Scheduling of visits within visit windows requires cautious planning to ensure there is no interruption to subject evaluation and study drug treatment.
- h Lipid panels are non-fasting and are to be drawn at a minimum of every 6months during the randomization withdrawal and LTE periods, or more frequently as needed, with mandated evaluations as detailed in the schedule of events.

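### Protocol Version 3.0 schedules no haematology or chemistry at RW Week 16, leaving 16 weeks without a scheduled check of the liver and neutrophil criteria

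*Protocol*

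**What the plan says.** Section 6.1.5 of Version 3.0 sets the RW visit pattern: "Visits will occur every 4 weeks, alternating TC/RN visits and clinic visits". The clinic visits are therefore Weeks 8, 16, 24 and every 8 weeks after that, plus EORW. In Section 13.1, Table 3, the row "Hematology, Chemistry Labs (Central" is marked at all of these except Week 16. At Week 16 the same table marks central CRP, body weight, PGIPS, PGA-PA, drug dispensing and in-clinic dosing.

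Section 4.3.2.1 contains criteria that only a laboratory result can trigger. Combined ALT or AST and bilirubin elevation, "with no underlying medical conditions to explain the elevated values", is a mandatory permanent stop. A low neutrophil count and "Isolated ALT or AST values" above 5 x ULN are items for which permanent or temporary discontinuation is to be strongly considered.

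Section 6.6 permits unscheduled safety laboratory tests at the investigator's judgement. Section 7.7.8 plans descriptive laboratory summaries by visit, and by treatment group in the RW period.

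Version 2.0, reproduced in the same file, marked Week 16 in Table 1–2. For the routine RW clinic visits its Section 6.1.3 said: "Obtain central laboratory samples for chemistry, hematology, and CRP".

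**The concern.** The discontinuation criteria depend on results that the schedule does not collect for 16 weeks in the middle of the randomised period. During that time some subjects recur, and those who meet the bailout criteria receive a new loading dose of rilonacept, possibly with NSAIDs and colchicine added. A fall in neutrophils or a rise in transaminases without symptoms would wait for the Week 24 sample unless something else led to a test.

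The RW period is also the only placebo-controlled part of the study. Subjects leave blinded placebo quickly under the design assumptions, so each omitted time point costs controlled laboratory data that later visits cannot replace. Version 3.0 makes Week 16 the time point of the three major secondary endpoints and drops the 24-week follow-up requirement, so the visit without laboratory tests is the more important of the two.

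**Working it through.** **Inputs.** Section 7.4: one-sided alpha 2.5%, power 90%, exponential times, "Median time to event (in weeks) in placebo 8", hazard ratio 0.244, 25 subjects per arm, 10% not reaching the RW period. Section 13.1: Tables 2, 3 and 4.

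**The plan's own figure.** Schoenfeld events = 4 x (1.960 + 1.282)² / (ln 0.244)² = 42.03 / 1.990 = 21.1, rounded up to 22, as stated. Enrolment = 50 / 0.90 = 55.6, or 56, as stated. The assumptions are therefore read as the sponsor used them.

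**Scheduled interval.**
- RW draws in force: Weeks 0 (RW baseline), 8, 24, 32, 40 and so on. Intervals: 8, 16, 8, 8 weeks.
- With a Week 16 mark: 8, 8, 8, 8, 8 weeks.
- LTE (Table 4): 12 weeks.
- With ±2-day windows at both ends, the gap is 16 x 7 ± 4 = 108 to 116 days.

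**First recurrences in the gap.** The placebo hazard is ln 2 / 8 per week and the rilonacept hazard is 0.244 times that. The share recurring between weeks a and b is S(a) − S(b).

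| Weeks | Placebo | Rilonacept | Subjects of 50 |
|---|---|---|---|
| 0–8 | 0.500 | 0.156 | 16.4 |
| 8–16 | 0.250 | 0.131 | 9.5 |
| 16–24 | 0.125 | 0.111 | 5.9 |
| 8–24 | 0.375 | 0.242 | 15.4 |

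For Weeks 8–24 this is 25 x 0.375 = 9.4 placebo and 25 x 0.242 = 6.1 rilonacept subjects, about 15 of 50 (31%). It is an upper bound on re-loading with bailout rilonacept, because bailout also requires pain ≥4 and CRP ≥1 mg/dL, and because the RW period may close first.

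**Recurrence-free subjects at each possible draw.**
- Placebo: S(8) = 0.50, S(16) = 0.25, S(24) = 0.125, which is 12.5, 6.3 and 3.1 of 25.
- Rilonacept: 1 − 0.156 = 0.844, then 0.844 − 0.131 = 0.713, then 0.713 − 0.111 = 0.602.

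If every recurrence leads to bailout, these are also the shares still on blinded drug. Subjects whose recurrence does not meet the bailout criteria stay on blinded drug and would raise them. In the placebo arm, Week 16 holds twice as many recurrence-free subjects as Week 24.

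**Version comparison.** Version 2.0 had the Week 16 draw in both table and text. The Version 3.0 summary of changes (Section 13.3) says that the move to a new template altered no study content unless specified. It lists the analysis trigger, the LTE extension and minor administrative and editorial changes, and no reduction in laboratory tests. A difference between versions is not itself an error. Here it shows only that the blank cell has no stated reason.

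**The case against.** The strongest reply is that no passage of Version 3.0 requires laboratory tests at every RW clinic visit. Section 6.6 simply defers to Section 13.1, so the blank cell contradicts nothing in the current text and may be deliberate. The summary of changes covers major changes only and need not list every cell. This stands, which is why the fix offers the sponsor the choice of giving a reason.

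A reader might infer more than the documents support:

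- **That the criteria go unchecked or cannot operate.** Section 6.6 permits unscheduled tests, adverse events are reviewed at every 4-weekly visit, and EOT and EORW visits include the draw. The RW period is event-driven, so EORW can fall inside the gap. What is missing is a scheduled check. EORW also falls at a different time since randomisation for each subject, so it does not replace a by-visit time point.
- **That the neutrophil and isolated ALT/AST items are stopping rules.** Only the combined liver criterion is mandatory.
- **That the RW period has the sparsest safety laboratory tests in the study.** It has two draws in its first 24 weeks, as does the LTE (Weeks 12 and 24), and is 8-weekly after that. Only the single interval is the longest.
- **That no creatinine would be available.** Section 6.6.3 allows creatinine with the point-of-care CRP device, which is the preferred local CRP method at a recurrence visit. That panel has no transaminases, bilirubin or neutrophils.
- **That the recurrence visit is also in error.** Under "PERICARDITIS RECURRENCE ASSESSMENT", Table 5 marks no haematology or chemistry, and Section 6.1.4 lists only "Obtain central laboratory samples for PK, ADAs, and biomarkers" besides CRP. Version 2.0 was the same, and no passage requires more. Adding tests there would be a preference, and it is not requested.

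The numbers are also modest. More first recurrences are expected in Weeks 0–8 (16.4 of 50) than in the gap, and a Week 8 draw follows those.

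**Conclusion.** The point holds in a limited form. RW Week 16 is the only RW clinic visit without scheduled haematology and chemistry, which leaves 16 weeks without a scheduled check of the Section 4.3.2.1 liver and neutrophil criteria. That is twice any other RW interval and longer than the 12 weeks of the LTE. The provision for unscheduled tests narrows the risk but does not remove it, because an abnormality without symptoms gives no reason to order one.

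Up to about 15 of 50 subjects have a first recurrence in the gap. On placebo, about 6 of 25 remain recurrence-free at Week 16 against about 3 of 25 at Week 24, so the descriptive by-arm laboratory summary gives up its better populated later time point. These counts rest on the protocol's exponential assumption, 8-week placebo median, hazard ratio of 0.244 and 25 per arm, with every subject followed to the visit. The length of the gap depends on none of these. The effect on the primary analysis is nil. This is an inexpensive improvement to safety detection and to the controlled laboratory data.

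**What to change.** Reconcile the haematology/chemistry row of Table 3 with Section 4.3.2.1 and with the other RW clinic visits. Either restore the Week 16 mark that Version 2.0 carried, or state in the protocol why it was removed and how the criteria are covered between Weeks 8 and 24. Record the choice in the summary of changes.

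Restoring the mark costs one or two extra tubes per subject, plus central laboratory processing, at a visit where central CRP is already drawn. It changes no dose, threshold or treatment rule, adds no visit and does not affect the efficacy analyses.

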5.2.2. Pediatric Subjects (≥12 and <18 years old)

Rilonacept: Loading dose 4.4 mg/kg administered as 2 SC injections, 2.2 mg/kg each (maximum 160 mg each) at RI baseline, followed by once-weekly SC injections of 2.2 mg/kg (maximum 160 mg). The volume of injections will be based on the subject's weight (Table 1).

Placebo (in RW): once-weekly SC injections with volume based on the subject's weight (Table 1 , maximum 2 ml).

Upon meeting protocol criteria for bailout rilonacept (Sections 3.1 and 6.2.3) in the RW period, subjects will be transitioned to open-label rilonacept 4.4 mg/kg administered as 1 (maximum 2 ml) or 2 SC injections at the next scheduled study drug administration date, followed by once-weekly SC injections of 2.2 mg/kg (maximum 2 ml). The volume of injections will be based on the subject's weight (Table 1).

Study drug dose/volume will be calculated by the Investigator or pharmacist during site clinic visits based on body weight (as specified in Section 13.1) using a weight-based dosing chart in kilograms (Table 1).

Table 1: Study Drug Dose Volume (After Reconstitution) by Body Weight in Kilograms for Pediatric Subjects Aged ≥12 and <18 Years

Weight Range (kg)	Loading Dose Volume (ml)	Weekly Dose Volume (ml)
23.6 to 27.2	2 x 0.7	0.7
27.3 to 30.8	2 x 0.8	0.8
30.9 to 34.4	2 x 0.9	0.9
34.5 to 38.1	2 x 1.0	1.0
38.2 to 41.7	2 x 1.1	1.1
41.8 to 45.4	2 x 1.2	1.2
45.5 to 49.0	2 x 1.3	1.3
49.1 to 52.6	2 x 1.4	1.4
52.7 to 56.3	2 x 1.5	1.5
56.4 to 59.9	2 x 1.6	1.6
60.0 to 63.5	2 x 1.7	1.7
63.6 to 67.2	2 x 1.8	1.8
67.3 to 70.8	2 x 1.9	1.9
70.9 or greater	2 x 2.0	2.0

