5.3. Identity of Investigational Medicinal Product

Rilonacept (KPL-914) is the drug being evaluated in the current study. Refer to Section 1.3 for a detailed description of rilonacept's mechanism of action.

Study drug (rilonacept or placebo) is supplied in a single-use, 20 ml glass vial containing a sterile, white to off-white, lyophilized powder. Each vial is to be reconstituted with 2.3 ml sterile Water for Injection (WFI). A volume up to 2 ml can be withdrawn, which is designated to deliver up to 160 mg of rilonacept or up to 2 ml placebo for SC injection only. The resulting solution is clear, colorless to pale yellow, and essentially free of particulates.

Each rilonacept vial contains 220 mg of rilonacept lyophilized powder. After reconstitution with 2.3 ml sterile WFI, the rilonacept vial contains 80 mg/ml rilonacept, 40 mM histidine, 50 mM arginine, 3.0% (w/v) polyethylene glycol 3350, 2.0% (w/v) sucrose, and 1.0% (w/v) glycine at a pH of 6.5. No preservatives are present.

Each placebo vial contains lyophilized powder. After reconstitution with 2.3 ml sterile WFI, the placebo vial contains 40 mM histidine, 50 mM arginine, 3.0% (w/v) polyethylene glycol 3350, 2.0% (w/v) sucrose, and 1.0% (w/v) glycine at a pH of 6.5. No preservatives are present.

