6.1.6. End of Randomized Withdrawal and LTE Baseline (EORW and LTE Baseline Visits)

All subjects, including those that have had pericarditis recurrence or have permanently discontinued study drug will have an EORW visit at the end of the RW period. Upon completion of the EORW visit procedures those subjects who have not discontinued treatment previously will provide informed consent to participate in the LTE period. The LTE Baseline visit will be completed on the same day as the EORW visit. During the LTE subjects will return to the site every 12 weeks for up to 24 months thereafter from the first dose of open-label rilonacept in the LTE. Refer to Section 13.1 for a comprehensive list of procedures in the Schedule of Activities for these visits.

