6.3.1. Physical Examination

A full physical examination should include at minimum an evaluation of vital signs, head, eyes, ears, nose, and throat as well as cardiovascular, dermatological, musculoskeletal, respiratory, GI, genitourinary, and neurological systems. The decision to perform examination of genitourinary system should be guided by clinical judgement. Body weight and height will be measured as per Section 13.1 and will be recorded in the eCRF. Any abnormality identified at baseline should be recorded on the medical history and physical

examination eCRFs. At selected visits as specified in Section 13.1, an abbreviated physical examination will be performed to evaluate vital signs, lung and heart sounds, including evaluation for pericardial rub.

At all visits at the study site, limited symptom-directed physical examinations may need to be performed in order to determine changes from baseline or abnormalities and should be recorded in the subject's trial notes. New or worsened abnormalities should be recorded as AEs on the Adverse Event eCRF.

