IWRS Subject Status Update	X	X								X
IWRS Weight Input (pediatric only)		X								X
IWRS Drug Dispensing		X		X				X		X
In Clinic Study Drug Administration ^o		X ⁿ						X		X
Outpatient Study Drug Administration ^o					WEEKLY					
Study Drug Compliance Review		X			X	X	X	X	X	X
Clinical Response Evaluation										X ^p
Adverse Event Reporting ^l	X	X		X	X	X	X	X	X	X

a The screening and enrollment visit can be combined.

b Scheduling of visits within visit windows requires cautious planning to ensure there is no interruption to subject evaluation and study drug treatment.

c Full physical examination includes at minimum evaluation of vital signs, head, eye, ear, nose, and throat as well as cardiovascular, dermatological, musculoskeletal, respiratory, GI, genitourinary, and neurological systems. The decision to perform examination of genitourinary system should be guided by clinical judgement.

d Abbreviated physical examination includes at minimum evaluation of vital signs, lung and heart sounds, including evaluation for pericardial rub.

e ECHO is required to be obtained according to the central core lab parameters and then read locally and submitted to the central core lab for separate review and analysis.

f Both a documented CRP ≥ 1.0 mg/dL AND a pericarditis pain level of ≥ 4 is required 7 days prior to and including the Run-In Baseline visit. These are not required to occur on the same day.

g Subjects missing ≥ 4 daily pain measurements during the 7 days prior to and including the Randomization Withdrawal baseline visit will be unable to proceed to randomization due to lack of data required for treatment response evaluation.

h Lipid panels are non-fasting and are to be drawn at a minimum of every 6months during the randomization withdrawal and LTE periods, or more frequently as needed, with mandated evaluations as detailed in the schedule of events.

i Applicable to 24-hour post dose PK sub-study participants only.

j For women of child bearing potential - urine pregnancy testing can be repeated as needed throughout the course of the study and serum pregnancy can be drawn as needed; urine pregnancy is required to be performed at enrollment and 6 weeks after the last dose of study drug.

k Pharmacogenomics informed consent and subsequent sampling can be performed at any time in the study however, it is preferable to have this completed at the beginning of the study.

- l Adverse event reporting begins following the subject providing informed consent.

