- v Study drug administration to occur only after subject provides informed consent for the open-label extension period.

Table 4: Study Schedule of Activities – Long Term Extension Treatment Period

Trial Period	LONG TERM EXTENSION (up to 24 months)			
	Long Term Extension Treatment (up to 24 Months) ^m			
Visit Name	LTE Week 12	LTE Week 24	LTE Every 12 Weeks	LTE 18-month Assessment ^{aa}
Visit Window ^b (days)	+/- 2	+/- 2	+/- 2	+/- 45
Visit Type	Clinic	Clinic	Clinic	Clinic
Concomitant medications	X	X	X	X
Pericarditis Concomitant medications	X	X	X	X
Full Physical Examination ^c		X		X
12-Lead ECG		X		X
Echo ^c		X		X
MRI		X ^z		X ^z
EQ-5D		X		
SF-36		X		
ISI		X		
PGIPS	X	X	X	
PGA-PA	X	X	X	
Hematology, Chemistry Labs (Central)	X	X	X	
Lipid Panel (Central) ^h		X		
CRP (Central)	X	X	X	X
PK (Central) ^s		X		X
ADA (Central) ^s		X	X ^{bb}	
Biomarkers (Central)		X		
Urine Pregnancy ^j (Local or Central)		X		X
Urinalysis		X		
IWRS Subject Status Update		X		X
IWRS Weight Input (pediatric only)	X		X	X
IWRS Drug Dispensing	X	X	X	X
In Clinic Study Drug Administration ^o	X	X	X	
Outpatient Study Drug Administration ^o	WEEKLY			
Study Drug Compliance Review	X	X	X	X
Assessment of Pericarditis Recurrence	X	X	X	X
Adverse Event Reporting ^l	X	X	X	X

- a The screening and enrollment visit can be combined.
- b Scheduling of visits within visit windows requires cautious planning to ensure there is no interruption to subject evaluation and study drug treatment.
- c Full physical examination includes at minimum evaluation of vital signs, head, eye, ear, nose, and throat as well as cardiovascular, dermatological, musculoskeletal, respiratory, GI, genitourinary, and neurological systems. The decision to perform examination of genitourinary system should be guided by clinical judgement.
- e ECHO is required to be obtained according to the central core lab parameters and then read locally and submitted to the central core lab for separate review and analysis.
- h Lipid panels are non-fasting and are to be drawn at a minimum of every 6 months during the randomization withdrawal and LTE periods, or more frequently as needed, with mandated evaluations as detailed in the schedule of events.
- j For women of child bearing potential - urine pregnancy testing can be repeated as needed throughout the course of the study and serum pregnancy can be drawn as needed; urine pregnancy is required to be performed at enrollment and 6 weeks after the last dose of study drug.

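### Minor: Table 4 dispenses drug at LTE Week 24 without a paediatric weight input, so the last scheduled dosing weight can be 24 weeks old by Week 36

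*Protocol*

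**What the plan says.** Section 5.2.2 doses subjects aged 12 to 17 by weight, using the bands in Table 1. It states: "Study drug dose/volume will be calculated by the Investigator or pharmacist during site clinic visits based on body weight (as specified in Section 13.1"). Section 6.3.1 defers to the same place: "Body weight and height will be measured as per Section 13.1 and will be recorded in the eCRF". The schedule in Section 13.1 therefore decides when a dosing weight is due.

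Section 6.1.6 sets the LTE visit interval: "During the LTE subjects will return to the site every 12 weeks for up to 24 months thereafter". Table 4 has four columns: Week 12, Week 24, every 12 weeks, and the 18-month assessment. The row "IWRS Drug Dispensing" is marked in all four. The weight row, "IWRS Weight Input (pediatric only"), reads in full "IWRS Weight Input (pediatric only) X X X", three marks for four columns, and the blank is at Week 24. Table 4 has no body weight row, and its footnote defining the full physical examination done at Week 24 does not list weight.

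In Table 3 (randomized withdrawal) every dispensing visit has a weight input, including the end-of-period visit that serves as LTE baseline. In Table 5 the recurrence visit has both. In Table 2 (run-in) drug is dispensed at Day 4 and Week 6 without a new weight, but weights are taken at run-in baseline and Week 12.

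**The concern.** LTE Week 24 is the only scheduled dispensing visit at which the schedule lets the dosing weight become more than 12 weeks old. It looks like a carry-over rather than a decision. In superseded v2.0, LTE Week 24 was the last visit of the treatment period and had neither dispensing nor weight input. Version 3.0 extended the LTE to 24 months and added dispensing there, but not the weight, and gives no reason.

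At stake is the accuracy of weight-based dosing in growing adolescents during one 12-week open-label supply. A site that follows the schedule exactly has no instruction to weigh them at that visit.

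**Working it through.** The protocol states no figure for the age of a dosing weight, so there is none to reproduce. The check has four steps.

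**1. Intervals between scheduled weight inputs (Tables 2 to 4, nominal weeks)**

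| Period | Weight inputs at week | Longest gap |
|---|---|---|
| Run-in | 0, 12 | 12 |
| Randomized withdrawal | 0, 8, 16, 24, then every 8 | 8 |
| LTE as written | 0, 12, 36, 48, ... | 36 − 12 = 24 |
| LTE with Week 24 marked | 0, 12, 24, 36, ... | 12 |

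With the two-day windows at each end, the LTE gap can reach 24 × 7 + 4 = 172 days.

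**2. Visits that can shorten the gap**

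A recurrence visit between LTE Weeks 12 and 36 does so. So can the 18-month assessment, whose footnote reads "Visit to occur 18 months from most recent documented recurrence". Eighteen months is 78 weeks, so the assessment falls at LTE Week w when the last recurrence was 78 − w weeks before LTE baseline.

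- w = 36 gives 42 weeks, and w = 12 gives 66 weeks.
- The 45-day window (6.4 weeks) widens this to about 36 to 72 weeks.
- A weight at Week 20, for example, is 36 − 20 = 16 weeks old at Week 36.
- A subject who enters the LTE straight from the 12-week run-in would reach this assessment at about LTE Week 66 (78 − 12), too late to help.

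**3. Growth against band width**

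Table 1 has 13 bands below 70.9 kg: (70.9 − 23.6)/13 = 3.64 kg each. One step is 0.1 ml × 80 mg/ml = 8 mg. Growth rates are not in the protocol; 3 and 6 kg per year are assumed.

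- Over 12 weeks: 3 × 84/365.25 = 0.69 kg, or 6 × 84/365.25 = 1.38 kg.
- Over 24 weeks: 1.38 or 2.76 kg. Both are below one band width, so nobody is two bands low.

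**4. Lowest dose the schedule can produce at Week 36**

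Take a subject at the top of a band when last weighed. The last weighing is at Week 12 as written, or at Week 24 with the fix.

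| Band | Growth | Last weighed Week 12 | Last weighed Week 24 | Drop |
|---|---|---|---|---|
| 0.7 ml (56 mg), top 27.2 kg | 3 kg/y | 56/28.58 = 1.96 | 56/27.89 = 2.01 | 0.05 mg/kg |
| 0.7 ml (56 mg), top 27.2 kg | 6 kg/y | 56/29.96 = 1.87 | 56/28.58 = 1.96 | 0.09 mg/kg |
| 1.9 ml (152 mg), top 70.8 kg | 3 kg/y | 152/72.18 = 2.11 | 152/71.49 = 2.13 | 0.02 mg/kg |
| 1.9 ml (152 mg), top 70.8 kg | 6 kg/y | 152/73.56 = 2.07 | 152/72.18 = 2.11 | 0.04 mg/kg |

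The drops run from 0.02/2.13 = 1% to 0.09/1.96 = 5%. At the time of weighing, the lightest band already spans 56/27.2 = 2.06 to 56/23.6 = 2.37 mg/kg.

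These drops describe the floor of the schedule. An individual who has crossed a band edge is a full 8 mg short of the next band, and one who has not is unaffected. As an illustration only, with weights also assumed uniform from 23.6 to 70.8 kg, the mean share one band low over the supply rises from 9.3% to 28.3% at 3 kg per year, and from 18.8% to 56.8% at 6 kg per year. That is 19 to 38 percentage points more, or on average 0.19 × 8 = 1.5 mg to 0.38 × 8 = 3.0 mg per weekly dose.

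**The case against.** The strongest reply is that use of the old weight is inferred. A reader might conclude that the blank cell makes adolescents receive a dose based on a 24-week-old weight. The protocol does not support that. Section 5.2.2 has the Investigator or pharmacist work out the volume at clinic visits, and LTE Week 24 is one. Section 5.3 says of each vial: "A volume up to 2 ml can be withdrawn". One vial therefore covers any weekly dose, and dispensing through the IWRS does not fix what is drawn up. Handling details sit in the Pharmacy Manual, which is not shown. A site may also re-weigh unprompted. All this stands, and it makes the dose effect conditional. It does not fill the cell, because Section 5.2.2 takes body weight as Section 13.1 schedules it.

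The effect is also small. Paediatric enrolment is capped at 20% of about 100, so at most 20 subjects. Even if all were under 70.9 kg and reached Week 24, the illustration gives about 4 to 8 more of them one band low (0.19 × 20 = 3.8; 0.38 × 20 = 7.6). The 160 mg cap gives 1.87 mg/kg to anyone weighing 160/1.87 = 86 kg, by design. The prescribing information appended to v2.0 reports, on limited data in CAPS patients aged 26 to 78, no marked effect of body weight between 50 and 120 kg on trough levels. These points stand and keep the matter minor.

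One could read the every-12-weeks column as covering Week 24, but Week 24 has its own column. The missing body weight row is not a separate defect, since a weight input already requires a weight.

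**Conclusion.** The point holds as a minor, cheap improvement. The blank cell and the nominal 24-week interval follow directly from the schedule. Not every weight-dosed subject meets the full interval: a recurrence visit or a suitably timed 18-month assessment shortens it.

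The dose effect depends on two things the protocol does not state: that the site uses the Week 12 weight, and that growth is 3 to 6 kg per year. On those terms nobody is more than one band low, and subjects at or above 70.9 kg are unaffected. The number of weight-dosed subjects who will reach LTE Week 24 is unknown. The period is open-label and follows the randomised comparison, so no efficacy conclusion is touched. The protocol does not show harm or meaningful underdosing.

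**What to change.** In Table 4, mark the paediatric weight-input row at LTE Week 24 and set the matching visit in the IWRS. This brings the longest nominal gap back to 12 weeks, the maximum elsewhere in the study. A separate body weight row in Table 4 is optional.

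The cost is one cell, one system setting, and a brief weighing of weight-dosed subjects at a visit where they are already in clinic for examination and dosing. The protocol gives no benefit from leaving the cell blank.
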